### 3.3 Exploratory Objective

- (1) **Objective:** To determine whether PD-1 response in responding patients is associated with common gut microbiota profile.

**Hypothesis:** PD-1 responders and non-responders have distinct gut commensal microbiota profiles; and that administration of single responder-derived FMT can reconstitute responder-associated microbiota profile in PD-1 non-responders.

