### 4.2.4.2 Biomarker Research

Biomarker endpoints include:

Analysis of bacterial taxa occurrence (within-sample and between-sample differences) in PD-1 responders, FMT responders and FMT non-responders.

Evaluation of anti-tumor T-cell responses, DC function/maturity by multi-parameter flow cytometry, multiplex immunohistochemistry, analysis of T-cell receptor (TCR) clonality/diversity and genetic mutation/expression studies (RNAseq, exome sequencing).

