### **8.5.3. Analysis of Secondary and Exploratory Endpoints**

The secondary objective is to investigate how FMT administration affects composition and function of T-cells and innate/adaptive immune system subsets. The pre-post difference of these endpoints will be compared between responders and non-responders with the two sided t-test or Wilcoxon rank sum test where appropriate. The exploratory objective is to determine whether PD-1 response in responding patients is associated with common gut microbiota profile. The same statistical analysis methods will be used as for the secondary endpoints.

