### **11.2 Correlative Studies**

Correlative studies will be performed using PBMCs and tumor tissues collected from the patients included in the study as detailed in the laboratory manual.

These studies will include:

- Multiparameter flow cytometry to evaluate T cell phenotype and function
- Nanosorting studies of tumor biopsies
- RNAseq and exome sequencing
- Studies of T cell repertoire
- Stool samples will be used for genomic evaluation of microbiota
  - 16S ribosomal RNA (rRNA) and metagenomic sequencing will be used to characterize the complexity of the human microbiome in the stool and at multiple body sites. 16S rRNA gene sequencing is a well-established method for studying phylogeny and taxonomy of samples from complex microbiomes or environments that are difficult or impossible to study.

Prior biopsy samples including primary tumor shave/excision biopsies, sentinel lymph node biopsies, completion lymph node dissection samples will be requested from pathology. Prior tissue obtained to establish metastatic disease, as part of definitive surgical management or as part of standard of care testing prior to current therapy will also be requested. These samples will be used for immunohistochemical (IHC) and RNA sequencing studies to evaluate immune responses and gene signatures associated with improved clinical outcome.

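### Section 8.5.3's two-sample test of pre-post change does not test the between-sample, reference-group or reconstitution questions in the microbiome objective, and no multiplicity control is stated

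*Combined protocol and SAP*

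**What the plan says.** The analysis plan for secondary and exploratory endpoints is one short paragraph, Section 8.5.3. For the immune endpoints, "The pre-post difference of these endpoints will be compared between responders and non-responders", using a two-sided t-test or Wilcoxon rank sum test as appropriate. For the gut microbiota objective it adds only: "The same statistical analysis methods will be used as for the secondary endpoints".

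The questions are set elsewhere:

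- Section 4.2.4.2 lists "Analysis of bacterial taxa occurrence (within-sample and between-sample differences) in PD-1 responders, FMT responders and FMT non-responders".
- Section 3.3 states two hypotheses: that "PD-1 responders and non-responders have distinct gut commensal microbiota profiles", and that "administration of single responder-derived FMT can reconstitute responder-associated microbiota profile in PD-1 non-responders".
- Section 11.2 names the assay: "16S ribosomal RNA (rRNA) and metagenomic sequencing will be used to characterize the complexity of the human microbiome".
- The study calendar notes and Section 7.1.2.7 schedule stool at screening, weekly in cycles 1 to 8, and every 6 weeks afterwards.

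These documents give no diversity or distance measure, no choice of post-FMT sample, no significance level for these tests, no number of taxa, and no family-wise or false-discovery control.

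**The concern.** The stated test takes one change score per patient and asks whether two groups of recipients differ in it. The listed questions have a different shape. One involves a reference group that never receives FMT. One involves quantities that belong to pairs of samples. One asks whether recipients as a whole come to resemble their donor. None of these is a responder-versus-non-responder contrast in change.

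Sequencing also produces many features, and the plan is silent on how many will be tested and how error will be controlled. Conversion of the microbiome is the premise of the trial, so a reported responder profile would be one of its main scientific products. At stake is the credibility of that product, not the decision on efficacy.

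**Working it through.** **1. Stated figures.** The documents give no operating characteristic for the microbiome analysis. The only ones stated are for the primary rule in Section 8.5.1.2: 13 then 20 patients, stop at 0 responses, success at 3 or more, response rates 5% and 25%. The formula is the sum over x = 1 to 13 of P(X1 = x) × P(X2 ≥ 3 − x), with X1 ~ Bin(13, p) and X2 ~ Bin(7, p).

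- p = 0.05: 0.0736 (stated 0.07).
- p = 0.25: 0.903 (stated 90%).

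Both reproduce. Their relevance here is group size: 3 responders of 20 is the success boundary, and 20 × 0.25 = 5 are expected at the target rate.

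**2. Method set against question.**

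| Question | Source | Does the stated test address it? |
|---|---|---|
| Change in within-sample diversity, FMT responders vs non-responders | 4.2.4.2 | Yes: one value per patient |
| PD-1 responders as a group | 4.2.4.2 | No: donors receive no FMT, so have no pre-post difference |
| Between-sample differences | 4.2.4.2 | No: pairwise distances share samples and are not one independent value per patient |
| Distinct profiles | 3.3 | Not as change: this is a contrast of levels, and differencing removes baseline level |
| Reconstitution of the donor profile | 3.3 | No: see step 3 |

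**3. Reconstitution.** Let d_i be patient i's change in distance to the donor, post minus pre. Reconstitution says the mean of d_i is below 0 over recipients. The stated test examines mean(d | responders) − mean(d | non-responders). If every recipient moves by the same amount, d_i = −c, the contrast is −c − (−c) = 0. The hypothesis would be true and the test would show nothing.

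**4. Time point.** Four 3-week cycles precede first restaging, so 4 × 3 = 12 weekly stool samples are scheduled by then. Section 8.5.3 does not say which is the post sample or how repeated samples are combined.

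**5. Multiplicity.** Assumptions, none of them stated in the documents: taxa tested one by one, 5% two-sided, no true differences. Expected false taxa = 0.05 × m. Chance of at least one, if independent, = 1 − 0.95^m.

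| m taxa | Expected false | Chance of at least one |
|---|---|---|
| 20 | 1 | 64% |
| 50 | 2.5 | 92% |
| 100 | 5 | 99.4% |
| 200 | 10 | >99.9% |

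The exact Wilcoxon test is discrete. At 3 vs 17 its attained size is 0.040, so the expected counts are about 0.8, 2.0, 4.0 and 8.1. With one responder the smallest p is 2/20 = 0.10, so no taxon can reach 5%.

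**6. What adjustment leaves.** Smallest exact two-sided Wilcoxon p = 2/C(20, r).

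- r = 3: 2/1140 = 0.00175.
- r = 5: 2/15504 = 0.00013.

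Under Benjamini-Hochberg at 5% with 200 taxa, the k-th threshold is 0.05k/200 = 0.00025k. At 3 vs 17, 7 × 0.00025 = 0.00175 falls just short of 0.001754, so at least 8 taxa would all have to separate the groups perfectly. For the t-test and a 2-SD difference at 3 vs 17, power falls from 0.855 unadjusted to 0.287 (50 taxa) or 0.211 (100 taxa) under Bonferroni, which is stricter than Benjamini-Hochberg.

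**The case against.** The best defence is that Section 8.5.3 is brief rather than wrong. A responder-versus-non-responder contrast in recipients addresses part of the exploratory objective, and a diversity index suits the named tests. Section 4.2.4.2 sits under the rationale for endpoints and prescribes no joint three-group test. Applying the same methods could mean the same tests applied to levels, which would allow pairwise comparison with PD-1 responders. Section 11.2 refers detail of the correlative studies to a laboratory manual that is not among these documents. The objective is already labelled exploratory.

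Much of this stands. A reader might infer that the plan cannot answer the exploratory objective at all. It can answer part of it. But even the generous reading, tests on levels, leaves pairwise distances and reconstitution without a method.

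A reader might also infer that the taxa reported will be many and mostly false, or that ranking them by p-value is nearly uninformative. The documents do not support either. The absence of adjustment is read from silence. The 5% level, the number of taxa and taxon-by-taxon testing are all assumptions. The share of false findings depends on how many true differences exist, which the documents do not estimate. A smallest attainable p-value does not make a ranking uninformative, and Benjamini-Hochberg keeps the raw p-value order in any case.

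**Conclusion.** The concern holds in limited form. The method in Section 8.5.3 fits change in a one-value-per-patient measure. It does not test between-sample differences, comparison with the PD-1 responder group, or reconstitution of the donor profile, and nothing else in the documents supplies a method for these. That conclusion needs no numerical assumption.

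The multiplicity part is conditional. False taxa can be expected in proportion to the number tested: 1 to 10 for 20 to 200 taxa under the assumptions of step 5, fewer with the exact Wilcoxon test, and none with a single responder. The consequence is confined to how far the microbiome findings can be believed. The primary decision rule does not change, and the point is an improvement to the plan rather than a threat to the trial.

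**What to change.** Amend Section 8.5.3 as follows.

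1. **Reconstitution.** Name a distance measure and one post-FMT stool sample in advance. Test the within-patient change in recipient-to-donor distance from screening to that sample over all recipients, then compare that change between FMT responders and non-responders.
2. **Three groups.** Compare PD-1 responders, FMT responders and FMT non-responders on between-sample distance with a permutation test, using one sample per patient. If repeated samples are used, restrict the permutations to respect the patient: group labels move only with whole patients, and time labels only within a patient.
3. **Individual markers.** Within each family (taxa, flow cytometry, T-cell repertoire, RNA), report Benjamini-Hochberg adjusted values beside raw p-values and effect sizes. Describe the marker-level results as hypothesis-generating. Keep the immune endpoints as the declared secondary objective.
4. **Keep** the existing two-sample test for change in within-sample diversity.

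The cost is SAP wording and standard software. Item 1 also needs donor stool to be sequenced and each recipient linked to the donor used; listing PD-1 responders in Section 4.2.4.2 implies the sequencing, but the link should be stated. The real downside is that with 3 to 5 responders, few or no individual taxa may pass the adjusted threshold, which is why raw values and effect sizes should stay in the report.

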## **9.0 LABELING, PACKAGING, STORAGE AND RETURN OF CLINICAL SUPPLIES**

### **9.1 Investigational Product**

The investigator shall take responsibility for and shall take all steps to maintain appropriate records and ensure appropriate supply, storage, handling, distribution and usage of investigational product in accordance with the protocol and any applicable laws and regulations.

Pembrolizumab is supplied by the HCC pharmacy. FMT is manufactured as described in Section 4.2.3. No clinical supplies are provided by Merck.

### **9.2 Packaging and Labeling Information**

Clinical supplies will be affixed with a clinical label in accordance with regulatory requirements.

### **9.3 Clinical Supplies Disclosure**

This trial is open-label; therefore, the subject, the trial site personnel, the Sponsor and/or designee are not blinded to treatment. Drug identity (name, strength) is included in the label text; random code/disclosure envelopes or lists are not provided.

#### **9.4 Storage and Handling Requirements**

Clinical supplies must be stored in a secure, limited-access location under the storage conditions specified on the label.

Receipt and dispensing of trial medication must be recorded by an authorized person at the trial site.

Clinical supplies may not be used for any purpose other than that stated in the protocol.

#### **9.5 Returns and Reconciliation**

The investigator is responsible for keeping accurate records of the FMT infusates generated during the context of this study, the amount dispensed to and returned by the subjects and the amount remaining at the conclusion of the trial.

### **10.0 ADMINISTRATIVE AND REGULATORY DETAILS**

#### **10.1 Confidentiality**

The confidentiality of records that could identify subjects must be protected, respecting the privacy and confidentiality rules applicable to regulatory requirements, the subjects' signed ICF and, in the US, the subjects' signed HIPAA Authorization. The consent form must also include a statement that Merck and regulatory authorities have direct access to participant records. The rights, safety, and well-being of the study subjects are the most important considerations and should prevail over interests of science and society.

#### **10.2 Compliance with Financial Disclosure Requirements**

Study investigators will ensure compliance with US Food and Drug Administration (FDA) financial disclosure regulations as set forth in 21 CFR Part 54.

#### **10.3 Compliance with Law, Audit and Debarment**

The study may be evaluated by Sponsor or designee internal auditors and government inspectors who must be allowed access to CRFs, source documents, other study files, and study facilities. All audit reports will be kept confidential.

#### **10.4 Compliance with Trial Registration and Results Posting Requirement**

The data collected during this study are confidential and proprietary to Sponsor or designee. Any publications or abstracts arising from this study must adhere to the publication requirements set forth in the clinical trial agreement (CTA) governing Investigator participation in the study. These requirements include, but are not limited to, submitting proposed publications to Sponsor or designee at the earliest practicable time prior to submission or presentation and otherwise within the time period set forth in the CTA.

#### **10.5 Data Safety Monitoring Plan**

Sponsor-Investigator, sub-investigators, regulatory, CRS management, clinical research coordinators, clinical research associates, data managers, and clinic staff meet monthly in Melanoma Center Data Safety Monitoring Boards (DSMB) to review and discuss study data to include, but not limited to, the following:

- a. Serious adverse events
- b. Subject safety issues
- c. Recruitment issues
- d. Accrual
- e. Protocol deviations
- f. Unanticipated problems
- g. Breaches of confidentiality

Under the terms of the Food and Drug Administration Modernization Act (FDAMA) and the Food and Drug Administration Amendments Act (FDAAA) (21 CFR 312.50, 21 CFR 312.56), the Sponsor of the trial is solely responsible for determining whether the trial and its results are subject to the requirements for submission to the Clinical Trials Data Bank, <http://www.clinicaltrials.gov>. Information posted will allow subjects to identify potentially appropriate trials for their disease conditions and pursue participation by calling a central contact number for further information on appropriate trial locations and trial site contact information.

Minutes from the DSMB meetings are available to anyone unable to attend the center DSMB.

All toxicities encountered during the study will be evaluated on an ongoing basis according to the NCI Common Toxicity Criteria version 5. All study treatment associated adverse events that are serious, at least possibly related and unexpected will be reported to the IRB. Any modifications necessary to ensure subject safety and decisions to continue, or close the trial to accrual are also discussed during these meetings. If any literature becomes available which changes the risk/benefit ratio or suggests that conducting the trial is no longer ethical, the IRB will be notified in the form of an Unanticipated Problem submission and the study may be terminated.

All study data reviewed and discussed during these meetings will be kept confidential. Any breach in subject confidentiality will be reported to the IRB in the form of an Unanticipated Problem submission. The summaries of these meetings are forwarded to the UPCI Data Safety and Monitoring Committee (DSMC), which also meets monthly following a designated format.

For all research protocols, there will be a commitment to comply with the IRB's policies for reporting unanticipated problems involving risk to subjects or others (including adverse

events). DSMC progress reports, to include a summary of all serious adverse events and modifications, and approval will be submitted to the IRB at the time of renewal.

Protocols with subjects in long-term (survival) follow-up or protocols in data analysis only, will be reviewed twice a year rather than monthly by the disease center DSMB.

Both the UPCI DSMC as well as the individual disease center DSMB have the authority to suspend accrual or further investigate treatment on any trial based on information discussed at these meetings.

All records related to this research study will be stored in a locked environment. Only the researchers affiliated with the research study and their staff will have access to the research records.

### **10.6 Quality Management System**

Independent monitoring of the clinical study for protocol and Guidelines on Good Clinical Practice compliance will be conducted periodically (i.e., at a minimum of annually) by qualified staff of the Education and Compliance Office – Human Subject Research, Research Conduct and Compliance Office, University of Pittsburgh.

The Investigator (i.e., the study site principal investigator) and the University of Pittsburgh and University of Pittsburgh Medical Center will permit direct access of the study monitors and appropriate regulatory authorities to the study data and to the corresponding source data and documents to verify the accuracy of this data.

### **10.7 Data Management**

The Investigator (i.e., the study site principal investigator) will maintain records in accordance with Good Clinical Practice.

The investigator will retain the specified records and reports for up to 2 years after the marketing application is approved for the investigational drug; or, if a marketing application is not submitted or approved for the investigational drug, until 2 years after investigations under the IND have been discontinued and the FDA so notified.

### **10.8 Institutional Review Board (IRB) Approval**

The investigator (i.e., the study site principal investigator) will obtain, from the University of Pittsburgh Institutional Review Board (IRB), prospective approval of the clinical protocol and corresponding informed consent form(s); modifications to the clinical protocol and corresponding informed consent forms, and advertisements (i.e., directed at potential research subjects) for study recruitment, if applicable.

The only circumstance in which a deviation from the current IRB-approved clinical protocol/consent form(s) may be initiated in the absence of prospective IRB approval is to eliminate an apparent immediate hazard to the research subject(s). In such circumstances, the investigator will promptly notify the University of Pittsburgh IRB of the deviation.

The University of Pittsburgh IRB operates in compliance with FDA regulations at [21 CFR Parts 50](#) and [21 CFR 56](#), and in conformance with applicable International Conference on Harmonization (ICH) Guidelines on Good Clinical Practice.

In the event that the University of Pittsburgh IRB requires, as a condition of approval, substantial changes to a clinical protocol submitted under an FDA-accepted IND application, or in the event of an sponsor's decision to modify the previously accepted clinical protocol, the sponsor will submit (i.e., in advance of implementing the change) a Protocol Amendment to the IND describing any change that significantly affects the safety of subjects, the scope of the investigation, or the scientific quality of the study. Examples of protocol changes requiring the submission of a Protocol Amendment include:

- Any increase in drug dosage or duration of exposure of individual subjects to the investigational drug beyond that described in the current protocol, or any significant increase in the number of subjects under study.
- Any significant change in the design of the protocol (such as the addition or deletion of a control group).
- The addition of a new test or procedure that is intended to improve monitoring for, or reduce the risk of, a side effect or AE; or the dropping of a test intended to monitor the safety of the investigational drug.

### **10.9 Ethical and Scientific Conduct of the Clinical Study**

The clinical study will be conducted in accordance with the current IRB-approved clinical protocol; ICH Guidelines on Guidelines on Good Clinical Practice; and relevant policies, requirements, and regulations of the University of Pittsburgh IRB, University of Pittsburgh and University of Pittsburgh Medical Center, Commonwealth of Pennsylvania, and applicable federal agencies.

### **10.10 Informed Consent**

The investigator (i.e., the study site principal investigator) will make certain that an appropriate informed consent process is in place to ensure that potential research subjects, or their authorized representatives, are fully informed about the nature and objectives of the clinical study, the potential risks and benefits of study participation, and their rights as research subjects. The investigator, or a sub-investigator(s) designated by the sponsor, will obtain the written, signed informed consent of each subject, or the subject's authorized representative, prior to performing any study-specific procedures on the subject. The date and time that the subject, or the subject's authorized representative, signs the informed consent form and a narrative of the issues discussed during the informed consent process will be documented in the subject's case history. The investigator or sub-investigator will retain the original copy of the signed informed consent form, and a copy will be provided to the subject, or to the subject's authorized representative.

The investigator will make certain that appropriate processes and procedures are in place to ensure that ongoing questions and concerns of enrolled subjects are adequately addressed and that the subjects are informed of any new information that may affect their decision to continue participation in the clinical study. In the event of substantial changes to the clinical

study or the risk-to-benefit ratio of study participation, the investigator will obtain the informed consent of enrolled subjects for continued participation in the clinical study.

